11.4. Efficacy Assessment

11.4.1. Number of enhancing lesions on T₁-weighted images taken on Week 36

Descriptive statistics of the number of enhancing lesions on T₁-weighted images taken on Week 36 and change from LAQ/5062 baseline and LAQ/5063 baseline to Week 36 will be presented by treatment group.

11.4.2. The number of new T₂ lesions on scan taken on Week 36

Descriptive statistics of new T₂ lesions measured on Week 36, with reference to the previous visit performed under LAQ/5062 protocol, will be presented by treatment group.

11.4.3. The volume of T₂ lesions on scan taken on Week 36

This endpoint will be analyzed using the same methodology outlined for the number of enhancing lesions on T₁-weighted images taken on Week 36 (see Section [11.4.1](#)).

11.4.4. The number of new hypointense lesions on enhanced T₁ scans taken on Week 36

Descriptive statistics of the number of new hypointense lesions on enhanced T₁ scans taken on Week 36, with reference to the previous visit performed under LAQ/5062 protocol will be presented by treatment group.

11.4.5. The proportion of subjects with no enhancing lesions on Week 36

The counts and percentages of subjects with no enhancing lesions on Week 36 will be presented by treatment group.

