	
first 3 months and at three-month intervals for the period of 24 months. Upon completion of the 24-month treatment period, visits will be performed at 6 months intervals thereafter, where, for the purpose of this study, a month is 30 days and a visit is defined as X months \pm 7 days.
 
During the open label phase subjects will be evaluated at study sites for the following scheduled visits:
 
Baseline (Month 0 / Termination visit of LAQ/5063 active double-blind phase (completion of the full 36 weeks or as requested by the Sponsor)), Month 1, Month 2, Month 3, Month 6, Month 9, Month 12, Month 15, Month 18, Month 21, Month 24, Month 30, Month 36, Month 42, Month 48, Month 54, Month 60 and every 6 months thereafter, until termination (may continue to participate in the study as long as the Sponsor continues the development of laquinimod 0.6 mg for RRMS) or early discontinuation.
 
Subjects who discontinue treatment for any reason will continue follow-up according to scheduled visits.
 
Magnetic resonance imaging (MRI) scans: this section is relevant only for the LAQ/5063 double-blind phase and the first 24 months of the LAQ/5063 Open-Label phase. During the active double-blind phase MRI will be performed at Baseline (Week 0 / Termination (Week 36) of Core Study LAQ/5062), and Week 36 (completion of the full 36 weeks of LAQ/5063 active double-blind phase or as requested by the Sponsor). For the open label phase MRI will be performed at baseline (Month 0 / Termination visit of LAQ/5063 active double-blind phase (completion of the full 36 weeks or as requested by the Sponsor), Month 12 and Month 24. Subjects who performed the MRI scan within a window of \leq 14 days, as part of the termination visit of LAQ/5063 active double-blind phase (completion of the full 36 weeks or as requested by the Sponsor), will not need to undergo another MRI scan for baseline visit of the open-label phase.
 
Neurological evaluations: during the active double-blind phase will be performed at Baseline (Week 0 / Termination (Week 36) of Core Study LAQ/5062), Week 12, Week 24 and Week 36 (completion of the full 36 weeks of LAQ/5063 active double-blind phase or as requested by the Sponsor). For the open label phase Neurological evaluations will be performed at Baseline (Month 0 / Termination visit of LAQ/5063 active double-blind phase (completion of the full 36 weeks or as requested by the Sponsor), Month 3, Month 6, Month 12, Month 18 and Month 24. Following Month 24 visit, neurological evaluations will be performed every 6 months thereafter. Subjects who performed the Neurological evaluations within a window of \leq 30 days, as part of the Termination visit of LAQ/5063 active double-blind phase (completion of the full 36 weeks or as requested by the Sponsor) will not need to undergo a Neurological evaluation for the baseline visit of the open-label phase.
 
Multiple Sclerosis Functional Composite (MSFC) will be assessed at Baseline (Week 0 / Termination (Week 36) of Core Study LAQ/5062), and Week 36

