Subjects will undergo MRI scans at Baseline (Week 0 / Termination (Week 36) of Core Study LAQ/5062), and Week 36 (Termination visit of LAQ/5063 active double-blind phase [completion of the full 36 weeks or as requested by the Sponsor]). For the open-label phase MRI will be performed at baseline (Month 0 / Termination visit of LAQ/5063 active double-blind phase (completion of the full 36 weeks or as requested by the Sponsor), Month 12 and Month 24. Subjects who performed the MRI scan within the past 14 days as part of the Termination visit of LAQ/5063 active double-blind phase (completion of the full 36 weeks or as requested by the Sponsor), will not need to undergo another MRI scan for baseline visit of LAQ/5063 OL.

Subjects who discontinue treatment for any reason will continue follow-up according to scheduled visits.

Unscheduled visits may be conducted whenever required due to various reasons, for example, AEs, or possible exacerbation.

Figure 1: Treatment Groups in MS-LAQ/5062 (Core Study) and the Double-Blind and Open-Label Phases of LAQ/5063 (Extension Study)

[figure not shown]

[figure not shown]
[figure not shown]
Figure 2: Study Flowchart for MS-LAQ/5062 Core Study

Figure 3: Study Flowchart for Open-Label Phase of LAQ/5063 Extension Study

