7.3.3. Termination Visit

Termination Visit (6) / (Week 36 ± 3 days) of LAQ/5063 Active Double-Blind Phase (Completion of the full 36 weeks or as requested by the sponsor), or any Termination or Early Discontinuation visit occurring as long as the Sponsor continues the development of laquinimod 0.6 mg for RRMS.

In the event of early discontinuation, standard termination procedures will be followed.

Early discontinuation is defined as withdrawal from the study prior to the completion of the full study period:

- Withdrawal prior to completion of 24 months of the first period of open label phase.
- Subjects that chose to continue to the second period of open label phase (additional 36 months), and did not complete this period.
- Subjects that chose to continue treatment from Month 60 as long as the Sponsor continues the development of laquinimod 0.6 mg for RRMS and did not complete this period.

Subjects who are discontinued from study treatment will be encouraged to continue all scheduled visits and procedures until completion of the study (with the exception of procedures associated with drug dispensing and accountability, pregnancy testing, and GFR estimation [including body weight measurement]).

Subjects who have completed 24 months of open label phase and chose not to continue to further extension of open label phase will be regarded as completers.

Subjects who have completed 60 months of the extension open label phase and chose not to continue to further extension of open label phase (as long as the Sponsor continues the development of laquinimod 0.6 mg for RRMS) will be regarded as completers.

The reason for discontinuation of therapy will be documented in the source documents and captured on the CRF. If there are several reasons for early discontinuation, the more severe will be chosen as the primary reason. In the event that laquinimod is discontinued early, an early termination visit should be completed as close to the last dosing date as possible.

Subjects who did not complete the 36 weeks of treatment of LAQ/5063 active double-blind phase until approval of amendment No 2 will be called for an a termination visit of the active double-blind phase as requested by the Sponsor to be switched to the open-label phase (LAQ/5063 OL)

In case a subject completed the 60 months OL period, but decided not to proceed with the further extension, he/she will be considered as completer.

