8. ASSESSMENT METHODS

8.1. Efficacy Assessment Methods

8.1.1. MRI Evaluations

The subjects will undergo MRI at Baseline (Week 0 / Termination (Week 36) of Core Study), and at Week 36 (termination)/early discontinuation visit.

The following parameters will be assessed:

- Number of T₁ GdE lesions
- Number of new T₂ lesions
- Volume of T₂ lesions
- Number of new hypointense T₁ lesions on enhanced T₁ scans ("black holes")

Steroid treatment for relapse (see Section 6.1) will not affect the schedule of MRI scans.

All MRI data will be interpreted by the MRI-Analysis Center (MRI-AC).

MRI scans can be performed within 4 days of each visit except for Week 36/ (termination) where the MRI scans are performed 4 days prior to this visit. For the MRI Protocol, see [Appendix 3](#).

This section is relevant only for the LAQ/5063 double-blind phase and the first 24 months of the LAQ/5063 Open-Label phase.

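### New-lesion counts labelled Week 36 may come from scan intervals shorter than 36 weeks, and Sections 11.4.2 and 11.4.4 have no rule for this and make no use of inter-scan time

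*Combined protocol and SAP*

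**What the plan says.** Section 11.4 ties all five MRI endpoints to Week 36. Two of them count lesions that appeared between two scans. New T2 lesions (11.4.2) are "measured on Week 36, with reference to the previous visit performed under LAQ/5062 protocol". For 11.4.4 the plan is "Descriptive statistics of the number of new hypointense lesions on enhanced T₁ scans taken on Week 36", with the same reference visit. Both are summarised descriptively by treatment group.

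The scan schedule gives Week 36 a wider meaning:

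- Synopsis, MRI scans: "Week 36 (completion of the full 36 weeks of LAQ/5063 active double-blind phase or as requested by the Sponsor".
- Section 5.1: "Week 36 (Termination visit of LAQ/5063 active double-blind phase [completion of the full 36 weeks or as requested by the Sponsor".
- Section 8.1.1 adds early discontinuation: "at Week 36 (termination)/early discontinuation visit".
- Section 7.3.3 names the visit "Termination Visit (6) / (Week 36 ± 3 days) of LAQ/5063 Active Double-Blind Phase", and its heading goes on to allow termination at the sponsor's request. It also says who is affected: "Subjects who did not complete the 36 weeks of treatment of LAQ/5063 active double-blind phase until approval of amendment No 2 will be called" in for the termination visit and moved to open label.

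The opening of Section 11 still describes 36 weeks of double-blind treatment. Section 11.3 defines one ITT cohort and no completer set. Section 11 gives no analysis window for MRI, no rule for scans taken before Week 36, and no use of the time between scans.

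**The concern.** A count of new lesions between two scans grows with the time between them. The extension baseline scan is the core-study termination scan, so the count covers the time spent in the double-blind phase. That time is shorter than 36 weeks for anyone called in under Amendment 2 or stopping early. If their counts enter the same mean as full 36-week counts, the mean is lower for a reason that has nothing to do with the drug, and the label Week 36 hides it.

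The place where this matters is the efficacy objective in the Synopsis and Section 4: a baseline-to-termination comparison within the former placebo group. A shortened interval makes new-lesion counts on drug look more favourable in that group, and balance between dose arms does not protect a within-group figure.

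**Working it through.** The protocol states no sample size, power or effect figure for these endpoints, so there is none to reproduce. The documents give neither the number called in early nor when they were scanned, so both are assumed and shown as ranges.

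**Inputs**

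- Full interval: 36 weeks (Section 11).
- f, the share of a group scanned before Week 36: assumed 10%, 25%, 50%.
- w, the mean inter-scan interval of those subjects: assumed 12, 18, 24 weeks.

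**Constant accrual.** Pooled mean ÷ true 36-week mean = (1 − f) + f × w/36, so the shortfall is f × (1 − w/36). Example: f = 25%, w = 18 gives 0.25 × 0.5 = 12.5%.

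| f | w = 12 | w = 18 | w = 24 |
|---|---|---|---|
| 10% | 6.7% | 5.0% | 3.3% |
| 25% | 16.7% | 12.5% | 8.3% |
| 50% | 33.3% | 25.0% | 16.7% |

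The shortfall goes to zero as f goes to zero or w approaches 36.

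**Front-loaded accrual.** Suppose the rate halves after Week 12. The share of the 36-week count reached by week w (w at least 12) is [12 + 0.5 × (w − 12)] / 24, that is 0.50, 0.625 and 0.75 at weeks 12, 18 and 24. The shortfall f × (1 − share) is 12.5%, 9.4% and 6.2% for f = 25%, and 25.0%, 18.8% and 12.5% for f = 50%.

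**Between groups.** Take a true ratio of 0.70 (assumed) and w = 18.

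- Equal f in both groups: the ratio stays 0.70.
- f of 25% and 35%: 0.70 × 0.875/0.825 = 0.74, or 0.70 × 0.825/0.875 = 0.66 the other way round.
- f of 20% and 40%: 0.70 × 0.90/0.80 = 0.79, or 0.70 × 0.80/0.90 = 0.62.

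**Does a rate repair it?** Use total lesions ÷ total inter-scan time × 36. With f = 25% and w = 18, the mean count is 0.875 of the full count and the mean time is 0.75 × 36 + 0.25 × 18 = 31.5 weeks, so 0.875/31.5 × 36 = 1.00. The shortfall is removed under constant accrual. Under the front-loaded pattern the mean count is 0.75 + 0.25 × 0.625 = 0.906, and 0.906/31.5 × 36 = 1.04. The rate is then about 4% too high where the raw mean is 9.4% too low.

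**The case against.** Several points on the other side are sound.

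- *Pooling is an inference.* A reader might take it as settled that short and full intervals are averaged. Section 11.4 does not say so. Read literally, it could restrict to scans truly taken at Week 36, and then the problem is missing data, not low counts. The repeated equation of Week 36 with the termination visit, the baseline-to-termination objective and the single ITT cohort make pooling the more natural reading, but no more than that.
- *Scope.* A reader might extend the point to all five MRI endpoints. Only 11.4.2 and 11.4.4 count lesions accrued between scans. Enhancing-lesion number, T2 volume and the lesion-free proportion are read from the scan itself (the first two also as changes from baseline). For these the issue is only unequal time on treatment.
- *Dose comparison.* A reader might infer a biased contrast between doses. Sponsor-requested termination is administrative, and former placebo subjects are re-randomized 1:1 in blocks stratified by center (Section 11.2). If early termination is balanced, ratios are unchanged.
- *Size.* Section 7.3.3 covers anyone short of 36 weeks, including a subject in week 35. Nothing shows that the intervals were only a few weeks, or that many subjects were affected.
- *Inference.* The analyses are exploratory and descriptive. No test or error rate is affected, so expressing the shift in standard errors would suggest a consequence that the plan does not contain.

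One further defence is weak. Appendix 4 mentions an analytical plan for MSFC scoring, and visit rules might sit there. But Section 18.4.2 says that the statistical analysis is the one defined in the protocol.

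What remains is that the scan label and the permitted scan time disagree, and the within-group level of two endpoints depends on interval length that the plan does not use.

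**Conclusion.** The point holds for the two new-lesion counts, 11.4.2 and 11.4.4. On the more natural reading, the within-group mean understates a true 36-week count by f × (1 − w/36). With the assumed ranges and constant accrual that is about 3% to 33%. It is less if accrual is front-loaded, and close to nothing if few subjects were scanned early. The actual size cannot be found from the documents.

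Between-group ratios are biased only if the share or timing of early scans differs by group. The within-group summary in former placebo subjects is affected whether or not the arms are balanced, as long as some of them were scanned early. The documents do not support the stronger claims that pooling is certain, that all five MRI endpoints read too low, or that the comparison of doses is distorted. The point should be corrected because the remedy is cheap and gives the reported mean a defined time base. It does not threaten any planned inference.

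**What to change.** 1. State in Section 11.4 that the endpoint scan is the double-blind termination scan, whether reached at the full 36 weeks, by sponsor request or by early discontinuation. For 11.4.1, 11.4.3 and 11.4.5 nothing more is needed.
2. Summarise inter-scan time by treatment group.
3. For 11.4.2 and 11.4.4, report new lesions per inter-scan time beside the raw counts, either as total lesions over total time or from a negative binomial model with log interval as offset.
4. Repeat these two endpoints in subjects scanned in the actual Week 36 window.

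The cost is a few sentences and a small set of extra tables. No new procedure is needed, and Appendix 3 already ties scan shipment to the scan date. The downside is that a rate assumes roughly constant accrual. This is least secure in former placebo subjects starting drug: if the effect builds over time, the rate runs somewhat high, as the 4% example shows. The Week 36-only table should therefore be read alongside it.

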11.4.6. The total number of confirmed relapses

Descriptive statistics of the total number of confirmed relapses will be presented by treatment group.

11.4.7. The proportion of relapse-free subjects

A subject that did not experience any relapse during the treatment period will be considered as a responder for the purpose of this analysis.

The counts and percentages of relapse-free subjects will be presented by treatment group.

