5.3. Inclusion Criteria

Subjects must meet all inclusion criteria in order to be eligible for Study 5063:

1. Subjects must have completed 36 weeks of treatment in the LAQ/5062 study and all termination visit activities in accordance with the protocol.
2. Women of child-bearing potential (for example women who are not postmenopausal or surgically sterilized) must practice two acceptable methods of birth control for the duration of the study and until 30 days after the last dose of study medication [acceptable methods of birth control in this open label extension phase include: intrauterine devices, barrier methods (condom or diaphragm with spermicide), and hormonal methods of birth control (e.g. oral contraceptive, contraceptive patch, and long-acting injectable contraceptive)].
3. Subjects must be willing and able to comply with the protocol requirements for the duration of the study.
4. Subjects must give signed, written informed consent prior to entering this extension study.

Inclusion Criteria For The Open-Label Phase

1. Subjects must have completed the 36 weeks of treatment (completion of the full 36 weeks or as requested by the Sponsor), of the active double-blind phase.
2. Women of child-bearing potential (for example women who are not postmenopausal or surgically sterilized) must practice two acceptable methods of birth control for the duration of the study and until 30 days after the last dose of study medication [acceptable methods of birth control in this open label extension phase include: intrauterine devices, barrier methods (condom or diaphragm with spermicide), and hormonal methods of birth control (e.g. oral contraceptive, contraceptive patch, and long-acting injectable contraceptive)].
3. Subjects must be willing and able to comply with the protocol requirements for the duration of the open-label phase (LAQ/5063 OL).
4. Subjects must give signed, written informed consent prior to entering the open-label phase (LAQ/5063 OL).

Inclusion Criteria for the LAQ/5063 OL open-label phase - further extension (after visit Month 24)

1. Subjects must have completed the 24 months of treatment of the first period of the open label phase

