7.1. Study Period

This is a continuation of the LAQ/5062 study as a multinational, multicenter, randomized, double-blind, parallel group study, assessing the safety, tolerability and efficacy of two doses of laquinimod in subjects with RRMS, followed by an open-label phase of laquinimod 0.6 mg daily (LAQ/5063 OL).

Subjects will enter this randomized, two active arms study immediately after completion of the LAQ/5062 core study. The blinding in both, core study (LAQ/5062) and its extension, will be maintained. Subjects will enter the open-label phase after completion of the Termination visit of LAQ/5063 active double-blind phase (completion of the full 36 weeks or as requested by the Sponsor).

The study duration is 36 weeks of double blind treatment (Week 0 [baseline] to Week 36 [termination]) or until the Sponsor's request. The duration of the open-label phase is as long as the Sponsor continues the development of laquinimod 0.6 mg for RRMS.

Subjects will be evaluated at study sites at Baseline (Week 0 / Termination (Week 36) of Core Study LAQ/5062), at Weeks 4, 8, 12, 16, 24, and 36 (Termination visit of LAQ/5063 active double-blind phase (completion of the full 36 weeks or as requested by the Sponsor).

For the Study 5063 open label extension phase, the visits will be at monthly intervals for the first 3 months and at three months intervals for the period of 24 months. Upon completion of the 24 month treatment period visits will be performed at 6 months intervals thereafter, where, for the purpose of this study, a month is 30 days and a visit is defined as X months \pm 7 days.

During the open label phase subjects will be evaluated at study sites for the following scheduled visits:

Baseline (Month 0 / Termination visit of LAQ/5063 active double-blind phase [completion of the full 36 weeks or as requested by the Sponsor]), Month 1, Month 2, Month 3, Month 6, Month 9, Month 12, Month 15, Month 18, Month 21, Month 24, Month 30, Month 36, Month 42, Month 48, Month 54, Month 60 and every 6 months thereafter, until termination (as long as the Sponsor continues the development of laquinimod 0.6 mg for RRMS) or early discontinuation.

Subjects who discontinue treatment for any reason will continue follow-up according to scheduled visits.

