11. STATISTICAL METHODOLOGY

A total of up to 264 subjects, randomized to treatment with 0.3 mg or 0.6 mg of laquinimod, are expected to be recruited into this double-blind, multi-national trial. The trial is planned for 36 weeks of double-blind treatment.

All data summaries in this trial will be presented by treatment group.

The statistical analyses of this study will be exploratory in nature. Continuous variables will be presented by descriptive statistics (mean, standard deviation, minimum, median and maximum values), by treatment group. For categorical variables treatment group counts and percentage from total subject population will be tabulated.

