11.3. Subjects Cohorts

A single data cohort is defined for this clinical trial. This cohort is:

ITT: Consists of all subjects who have been randomized to the study and received at least one dose of IMP. In accordance with the ITT principle, all subjects randomized will be kept in their originally assigned treatment group.

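### Relapse counts and the relapse-free share ignore time at risk, although the double-blind phase can end before 36 weeks, so a subject stopped early without a relapse counts as a responder

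*Combined protocol and SAP*

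**What the plan says.** **Relapse summaries.** Section 11.4.6: "Descriptive statistics of the total number of confirmed relapses will be presented by treatment group". Section 11.4.7: "A subject that did not experience any relapse during the treatment period will be considered as a responder for the purpose of this analysis", reported as counts and percentages. Neither section mentions time at risk, censoring or a minimum follow-up, and 11.4.7 does not say which phase its treatment period covers.

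**Length of the phase.** Section 11: "The trial is planned for 36 weeks of double-blind treatment". Section 7.1 is more flexible: "The study duration is 36 weeks of double blind treatment (Week 0 [baseline] to Week 36 [termination]) or until the Sponsor's request". Section 7.3.3 puts the early stop into practice: "Subjects who did not complete the 36 weeks of treatment of LAQ/5063 active double-blind phase until approval of amendment No 2 will be called" for a termination visit and moved to open label.

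**Analysis set.** The single cohort in Section 11.3 "Consists of all subjects who have been randomized to the study and received at least one dose of IMP", so a subject with short follow-up stays in the denominator.

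**Listed outcome.** Sections 1 and 4.1.3 list Relapse Rate as an efficacy measure. Section 11.4 contains no rate.

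**Status.** Section 11: "The statistical analyses of this study will be exploratory in nature".

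**The concern.** A relapse-free percentage has meaning only for a stated length of observation. Here the length can vary between subjects, through sponsor-requested stops and ordinary drop-out, and the responder rule takes no account of it. Someone observed for 12 weeks without a relapse counts the same as someone observed for 36. The error has a known direction within each group: the share is too high and the mean count too low as descriptions of 36 weeks.

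What is at stake is how the levels are read. Section 4 frames the efficacy objective as a baseline-to-termination comparison within the former placebo group. Section 11 specifies no comparison of core-study with extension relapses. A reader who made one would set a completed 36-week core period, which Section 5.3 requires for entry, against a possibly shorter extension period. That error would flatter active treatment, and similar shortening in both dose arms would not remove it.

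Section 11 plans no table of follow-up duration. EDSS summaries by visit (11.4.8, 11.4.9) would show part of the shortening, because EDSS is scheduled at Weeks 12, 24 and 36. How the drop-out table in 11.5.5 would count sponsor-requested stops is unclear. The open-label inclusion criterion in 5.3 reads as completion: "Subjects must have completed the 36 weeks of treatment (completion of the full 36 weeks or as requested by the Sponsor". Section 5.4 treats such a stop as an exempt form of premature discontinuation, and 7.3.3 describes these subjects as not having completed 36 weeks.

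**Working it through.** The plan gives no figure to reproduce: it states no relapse rate, no power calculation, and no number or timing of early stops. From the documents come the 36-week period and the ceiling of 264 subjects (Sections 11 and 11.1). Everything else below is assumed.

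**Model.** Constant relapse rate r per year; a fraction f of subjects stopped at week w.
- Relapse-free probability to week w: S(w) = exp(−r·w/52).
- Crude share under 11.4.7: (1 − f)·S(36) + f·S(w).
- Inflation: f·[S(w) − S(36)].
- Mean count relative to 36 weeks: 1 − f + f·w/36.

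**Stops at week 18**

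| r | S(36) | S(18) | S(18) − S(36) | f for +1 point | f for +5 points |
|---|---|---|---|---|---|
| 0.3 | 0.8125 | 0.9014 | 0.0889 | 11.2% (29.7 of 264) | 56.2% (148.5) |
| 0.5 | 0.7074 | 0.8411 | 0.1337 | 7.5% (19.8) | 37.4% (98.8) |
| 0.8 | 0.5747 | 0.7581 | 0.1834 | 5.5% (14.4) | 27.3% (72.0) |

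The last two columns are 0.01 and 0.05 divided by the fourth column.

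**Middle case (r = 0.5, f = 0.3, w = 18).** Share: 0.7074 + 0.3 × 0.1337 = 0.7475, so 70.7% becomes 74.8%. Mean count: 0.5 × 36/52 = 0.346 becomes 0.346 × (1 − 0.3 + 0.3 × 18/36) = 0.346 × 0.85 = 0.294.

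**Range (r 0.3 to 0.8, f 10% to 50%, w 12 to 24).** The smallest inflation is 0.6 points (r 0.3, f 10%, w 24) and the largest 12.8 points (r 0.8, f 50%, w 12). If rates vary strongly between subjects (gamma, shape 0.5), the range is 0.4 to 8.3 points.

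**Between arms.** With equal true rates, but 5% stopped at week 12 in one arm and 25% in the other, the spurious difference is 0.20 × [S(12) − S(36)]: 2.4 points at r = 0.3 and 4.7 points at r = 0.7. With equal stopping it is zero.

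**Does the remedy help when drop-out is informative?** Suppose 10% to 20% leave at week 12 and would then relapse at twice the rate (r 0.3 to 0.8).
- The plan's rule overstates the share by f·S(12)·[1 − exp(−2r·24/52)], which is 2.3 to 8.7 points.
- Kaplan-Meier overstates it by f·S(12)·[exp(−r·24/52) − exp(−2r·24/52)], which is 1.1 to 3.5 points.

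**Precision of a rate in the middle case.** Person-years: 264 × (0.7 × 36 + 0.3 × 18)/52 = 155.4, against 182.8 if everyone reached week 36. With 78 relapses the rate is 0.50 per year, exact 95% CI 0.40 to 0.63. With 132 subjects per dose and 39 relapses each it is 0.50 (0.36 to 0.69).

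**The case against.** **The analyses are exploratory and the size is unknown.** Both are true. No test, alpha or power figure is affected, and the upper end of the range needs half the subjects stopped at week 12 at a high relapse rate. This limits the weight of the point, but a descriptive percentage still has to say what period it describes.

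**Section 11.4.7 never claims a 36-week proportion.** Also true: the sections on enhancing lesions and T2 volume name Week 36, and this one names only the treatment period. This moves the defect without removing it. The term is undefined, while Section 11 plans 36 weeks.

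**Subjects are followed after stopping treatment.** Sections 5.1 and 7.1 say so, but the responder rule covers only the treatment period. Subjects stopped at the Sponsor's request move to open-label treatment, so later visits do not restore double-blind follow-up.

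**A separate plan may define the rate.** Appendix 4 refers to an analytical plan, there for MSFC scoring. The missing rate analysis is shown only for the document reviewed.

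Three stronger readings are tempting and not supported:
- *The tables conceal all shortening.* EDSS summaries by visit would reveal part of it, and Sections 5.4 and 7.3.3 do not treat a sponsor-requested stop as completion.
- *The plan leaves open whether a sponsor-requested MRI counts as Week 36.* Section 5.1 and the synopsis define the Week 36 scan to include that termination visit. At most, Section 11 is unclear about early-discontinuation scans.
- *Relapse onset dates are in the CRF.* Appendix 1 asks sites to estimate the onset date when arranging the visit; it does not establish that the date is recorded there.

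**Conclusion.** The point holds as a gap in method. Applied as written, 11.4.6 and 11.4.7 give a lower mean relapse count and a higher relapse-free share than a full 36 weeks would, whenever some subjects stop early; the plan expressly provides for such stops. The listed Relapse Rate has no analysis in Section 11.4.

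Confidence is high in the text and the direction, not in the size. The illustration of about 4 points (70.7% to 74.8%) rests wholly on an assumed rate, share and timing, and with few early stops the effect is negligible.

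A reader might infer that the 0.3 mg versus 0.6 mg comparison is biased. The documents do not support that: a stop tied to an amendment's approval date should shorten follow-up similarly in both arms, and nothing in the plan suggests otherwise. The consequence is confined to how two descriptive summaries are read. The change should be made, but no formal inference depends on it.

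**What to change.** - **11.4.6:** report confirmed relapses per person-year of double-blind treatment, with a 95% CI, as the listed Relapse Rate.
- **11.4.7:** define the treatment period as the double-blind phase. Beside the crude percentage, report the Kaplan-Meier relapse-free proportion at Week 36, censored at the double-blind termination visit. State that censoring is assumed non-informative. This is plausible for sponsor-requested stops and weaker for drop-out, since Section 7.3.4 lists lack of efficacy as a withdrawal reason.
- **Event date:** use relapse onset if it is recorded, otherwise the date of the relapse visit.
- **Follow-up:** add duration by treatment group, with sponsor-requested stops shown separately from Week 36 completers and other discontinuations, and say how 11.5.5 counts them.
- **MRI:** one sentence in Section 11 on whether early-discontinuation scans enter the Week 36 summaries.

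The cost is plan wording and about three tables from visit and relapse dates. The relapse-free figure may look slightly less favourable, and Kaplan-Meier reduces but does not remove bias from informative drop-out. Appendix 8 shows that the study is already in its open-label phase, so if double-blind results have been reported, the new tables must be labelled as added later.
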